### **WP3. Key informant interviews**

We will undertake in-depth, semi-structured interviews with individuals holding key positions within the relevant guideline issuing organisations and representatives of national competent authorities. Interviewer questions and prompts will attempt to confirm, clarify, and address gaps in relation to preliminary findings from the document analysis. In particular, we will investigate how organisations perceive their roles and responsibilities as to the dissemination of safety information, how these are embedded in clinical guidelines and will strive to identify potential factors influencing the decision of individual organisations to act on or communicate about a serious safety update via clinical guidelines.

The sequential planning of the WPs (see figure 2) uses the capacity of qualitative interviewing to explore subjective, non-observable dimensions of a phenomenon or object to gain a better understanding of the results from preceding content analysis. Whereas content analysis identifies and quantifies salient dimensions of the guidelines, key informant interviews explore the various processes through which the guidelines are produced and updated.

Interview transcripts will be constructed based on audio recording and filed notes taken during the interview. The transcripts will be analysed concurrently with conducting interviews in order to adjust the interview guide as new information is acquired. A purposive sampling method to ensure heterogeneity of participants will be used. The researchers will recruit stakeholders and medical specialists across different specialties to diversify the responses obtained and obtain general themes.

In WP3 we will conduct a purposeful sampling of organizations and individuals within the countries and therapeutic areas whom we will engage for interview. The purposeful sampling strategy will be based on organisational mapping (WP1) and document analysis (WP2) with the aim to capture variation in processes, roles and responsibilities for updating clinical guidelines. Purposeful sampling is a strategy that is widely used in qualitative research to ensure the identification and selection of information-rich cases and the optimal use of limited resources (17). This includes identifying individuals or organizations that are particularly knowledgeable about the object of research. Purposive sampling differs from probabilistic or random sampling strategies that are typically employed to ensure the generalizability of findings through the minimization of potential selection biases. Although both qualitative and quantitative sampling methods are employed to maximize efficiency and validity, qualitative methods are typically employed to achieve depth of understanding whereas quantitative methods are employed to achieve breadth of understanding. (Patton, 2002). That is, qualitative methods emphasize saturation (i.e., reaching a comprehensive understanding by continuing to sample until no new substantive information emerges) whereas quantitative methods emphasize on generalizability (i.e., ensuring that the information gained is representative of the population from which the sample was drawn).

In WP3, we employ sequential sampling strategy that combines inclusive criterion-based sampling and complementary maximum variation-based sampling (18). The sequence is as follows: First, we identify which organizations to include based on the mapping exercise in WP1. Second, we identify which individuals to recruit for participation based on inclusion criteria. Third, we complement the criterion-based sample with relevant organizations to ensure that maximum variation of cases is captured.

The inclusion criteria for the stakeholder engagement are: 1) the entity that authored a guideline of

interest identified in WP2. 2) an entity that includes a stakeholder which represents one of the therapeutic areas (Table 2). The criteria-based sample of organizations will be complemented by a sample of organizations that are not national competent agencies or specific to the therapeutic areas. This complementary sample enables the inclusion of perspectives and knowledge from organizations that have a coordinating function, that operate on a subnational level or that operate more downstream from clinical guideline developers.

The inclusion criteria for individual participants from guidelines developing entities are: 1) individuals who have knowledge and/or experience with updating and publishing the entities' guidelines, including the triggers, processes and timelines. 2) individuals who have experience with updating and/or publishing the specific guideline identified as relevant in WP2. 3) individuals who have experience and/or knowledge with RMMs and their integration into clinical guidelines. In case there are no national guidelines published for one or several case medicines we will engage with professionals that cover "the field of the medicines" and are "key opinion leaders" or that have experience with guideline development not necessarily related to the key case medicines in the study.

Information produced by these three WPs will provide the data needed to accomplish objective 3 of this study, which is to provide recommendations to regulators to engage with healthcare professional bodies and other responsible parties to strengthen the role of clinical guidelines in RMMs implementation. Previously unidentified guidelines and organizations that emerge in interviews in WP3 will be added to mapping in WP1 and WP2 and analysed accordingly.

As for recruitment strategy, a lack of response from contacted participants will be followed up by reminder email, subsequently reminder telephone call. In case of persistent non-response or rejection, a new contact person will be identified and contacted.

In order to assess transferability of findings to other disease areas, puts the onus on the reader to evaluate the methods, setting and findings, and decide whether they are transferable to their situation (19). To evaluate the transferability of results of this multi-case study, we will provide a thorough and in-depth description of the findings and the context in which these findings are situated. The transferability will be conceptual, i.e. a general picture can be painted of the key triggers for updating clinical guidelines across disease areas will be described explicitly in the findings.

## **9.2. Setting & study population**

### **9.2.1. Country**

The diffusion of emergent drug safety information will be studied in parallel in six European Member States spread across Europe. These include Denmark (5.8m inhabitants), Greece (10.4m inhabitants), Latvia (1.9m inhabitants), the Netherlands (17.1m inhabitants), Portugal (10.2m inhabitants) and Slovenia (2.1m inhabitants). Together these countries include an active population of 47.5 million European citizens, which are distributed over the four different geographic regions (North, East, West, South) across the European Union. These countries differ in their social and cultural aspects as well as with regards to the organisation of health systems and provision of care. Therefore, we expect that studying procedures in these countries will provide us with a broad view of processes for including RMMs in clinical guidelines in Europe.

### **9.2.2. Documents and materials**

For **WP1 and WP2**, we will study various types of documents and online materials (text) in each of the

six countries. For WP1, we have selected an initial set of health care professionals groups and organisations based on the products that are included in the five case study RMMs from the selection criteria stated in Table 2. The preliminary list of (national) entities shared by Member States (see Appendix III) will be included in WP1. This list will be augmented by organisations, entities, and expert groups in each country where the health care professionals (Table 2) are involved. This information will be collected via contractors' country networks and web searches. For WP2, we will analyse the identified clinical guidelines and assess if they include information on RMMs which will be noted in the coding WP2 framework (see also variables section 9.3). When RMMs are identified in clinical guidelines we will assess if a reference is made to where these originate from, e.g., from which key regulatory documents, publications, regulatory communications, public statements on regulatory actions, product information, these originate.

We will assess current versions as well as note the time elapsing between and RMM and update of a guideline, whenever possible. This will allow us to understand the timeframe from publication of the RMM until implementation into clinical guidelines, next to understanding of the process which will be assessed in WP3.

### **9.2.3. Key informants**

For WP3, we will use qualitative interviews (see 9.1, WP3 for approach), including representative key informants in the six countries, to provide a comprehensive overview of processes, facilitators and barriers for integrating information from RMMs in clinical guidelines. Per country, these can include:

National competent authorities (*at least 1* stakeholder per country)

Public sector organisations and health authorities which produce clinical guidance for healthcare professionals commonly involved in patients' treatment, either nationally or regionally (*at least 1* stakeholder per country, when possible). These will be found from a list generated in WP1.

Professional associations (or ad-hoc groups) which represent healthcare professionals commonly involved in the treatment, either nationally or regionally (*at least 1* stakeholder from each disease priority area per country, see section 7). These will be found from a list generated in WP1.

These stakeholders will be identified and contacted via professional, public and governmental organisations, as well as through the professional network of the researchers involved in this proposal.

### **9.2.4. Stakeholder recruitment (per country)**

Stakeholders will be recruited per country as indicated below.

*Denmark:* Stakeholders from national competent authorities/drug regulatory agencies will be recruited through direct contact with the Danish Medicines Agency (DKMA); stakeholders from public sector organisations and health authorities will be recruited through direct contact from the researchers; health care professionals, including general practitioners and clinical specialists will be recruited through existing networks and professional organizations via direct contact with the respective organisations as well as via newsletters (UCPH has participated in a number of research projects and research networks where medical specialists have been involved, among these general practitioners). UCPH is an active member of a large pharmacy practice-based research network with links to community and hospital pharmacies.

*Greece:* The process of recruitment of stakeholders and health care professionals requires a methodological recording of all the available relative organizations, entities, or persons whom the

Greek team can contact. A detailed table with the available organisations and their contact details will be provided from the Greek team to co-partners. Firstly, stakeholders from the national competent authority/drug regulatory agency, which is the Greek National Organization of Medicines (EOF) will be recruited through direct contact via emails sent by the Greek research team. The communication with the members of EOF will be mainly conducted via email and if it becomes necessary for the recruitment strategy will be done by phone. Stakeholders from public sector organizations and health authorities will be recruited through direct contact via emails and phones (when it becomes necessary due to limited time) from the research team; healthcare professionals, including general practitioners and clinical specialists relative to the objectives of the study will be recruited through existing networks and professional associations through direct contact with the respective associations via emails (DUTH has longstanding collaborations with the General Hospital of Alexandroupolis, which is one of the most recognized academic hospitals in Greece and plays a significant role in the North-Eastern part of Greece) and primary care units. Finally, the Greek team will record the output of every contact to the aforementioned table (reference only to the organisations not to specific persons), whether it was an affirmative response for the interview process or not.

*Latvia:* Stakeholders from national competent authority/drug regulatory agency will be recruited through direct contact with the State Agency of Medicines of Latvia (SAM of Latvia); stakeholders from public sector organisations and health authorities will be recruited through direct contact from the researchers; representatives of professional associations will be recruited through existing networks and professional organizations via direct contact. RSU, IPH has multiple collaborations with the above-mentioned institutions. These will be used to identify representatives of health authorities, professional associations etc for the initial contact.

*Netherlands:* Stakeholders from national competent authorities/drug regulatory agencies will be recruited through direct contact with the Dutch Medicines Evaluation board (UU has multiple ongoing collaborations); stakeholders from public sector organisations and health authorities will be recruited through direct contact by researchers based at the National Institute for Public Health and the Environment (RIVM); health care professionals, including general practitioners and clinical specialists will be recruited through existing networks and professional organizations via direct contact with the respective organisations as well as via newsletters (UU has longstanding collaborations with the University Medical Center Utrecht which is one of the largest academic hospitals in the Netherlands and the Netherlands Institute of Health Services Research, which operates a large research network of general practitioners. The Utrecht Pharmacy Practice Network for Education and Research is a part of the UU and operates a large pharmacy practice-based research network with links to community and hospital pharmacies (20).

*Portugal:* Stakeholders from national competent authorities/drug regulatory agency will be recruited through direct contact with the National Authority of Medicines and Health Products, I.P. (INFARMED, I.P.), with which the Faculty of Medicine (FMUP) has a direct collaboration. Stakeholders from public sector organisations and health authorities will be recruited through direct contact from the research team. Healthcare professionals, including general practitioners and clinical specialists will be recruited through existing networks and professional organizations/societies via direct contact. FMUP has several collaborations with Hospitals (namely São João University Hospital Center) and primary care units.

*Slovenia:* Stakeholders from national competent authorities/drug regulatory agencies will be recruited through direct contact with the Agency for Medicinal Products and Medical Devices of the Republic of Slovenia (JAZMP); stakeholders from public sector organisations and health authorities will be recruited through direct contact by researchers; health care professionals, including general practitioners and clinical specialists will be recruited through existing networks and professional organizations via direct contact with the respective organisations. Contacts will be established first by email and subsequently by telephone, if needed.

Members of the PRAC, assessors and advisors directly involved in the regulatory procedures for the included products will not be included in the stakeholder interviews. Interviewees will be asked prior to interview.

### **9.2.5. Disease priority areas**

The disease priority areas and active substances that will be included in this study for the TA specific objectives are presented in section 7.

## **9.3. Variables**

Information on exposures, outcomes and characteristics such as risk factors is not applicable for this study. This study will include information about the entities that issue, develop and/or update clinical guidelines identified in WP1 as well as information extracted from clinical guideline documents (document analysis, WP2). In addition, semi-structured interviews will be utilized to explore subjective, non-observable dimensions of social relations or work processes to supplement and extend understanding of the results from preceding document analysis (WP3).

### **WP1. Mapping of relevant organisations**

The following information will be registered for identified organisations (see also coding framework for WP1):

- **General information** about the entity (name, description, address, telephone number, website, contact person [if applicable], level of operation (international/national/regional/local level).
- Information about **membership** including type of entity (professional organisation, interprofessional platform, public authority, public or non-profit organisation, hospital, (group of) experts and other). For each type of entity the primary membership will be noted. For professional organisations, the type of health care provider is based on the case studies: general practitioners (valproate, fluoroquinolones, metformin, methotrexate), neurologists (fluoroquinolones valproate), psychiatrists (valproate), oncologists (Fluorouracil and related substances), orthopaedist (fluoroquinolones), gastroenterologists (methotrexate), internists (fluoroquinolones, metformin), geriatricians (fluoroquinolones), endocrinologists (metformin), rheumatologists (fluoroquinolones, methotrexate), dermatologists (methotrexate), nurses, pharmacists and others. When interprofessional platforms are regarded the type of professionals participating will be noted. For public authority: regulatory authority, ministry of health, other. For public and non-profit organisations, the following will be noted: Health technology assessment bodies, public health organisations, patient organisations, other.
- **Guidelines development** including if identified organisations publish guidelines (yes/no), information on developer (developed by organisations, developed by other organisations), the type of document (clinical practice guideline, position paper, educational resource for HCPs, clinical recommendation lists, other).
- Any **other relevant information** not covered by coding matrix.

## **WP2. Content analysis of clinical guidelines**

The following information will be registered for identified clinical guidelines:

- **General information** on the clinical guideline (name, version number & version date (national level publication), number & version date (only applicable to international guidelines, international level publication) frequency of updating (number/months), website/link, funding reported to be received (yes/no) and country;
  
- Information about the **target audience** of the guideline (coverage [country, regional, other, not specified], setting [primary care, secondary care, both, other, not specified], and medical specialty [general practitioners, neurologists, psychiatrists, oncologists, orthopaedists, internists, geriatricians, endocrinologists, rheumatologists, dermatologists, gastroenterologists, nurses, pharmacists and others), the **population** to whom the guideline applies (children [0-9 years], adolescents [10-17 years], adult [18-64 years], seniors [65 and older], pregnant females, other), and treatment (active substance: valproate, fluoroquinolones), methotrexate, metformin, fluorouracil and related substances) and **therapeutic area** based on approved indications (neurology, psychiatry, diabetes, infections, immunology, oncology, other);
  
- **Information about the RMM** included in guideline: information on case study medication safety mentioned (yes/no), content of safety information (original language and English translation), RMM mentioned (yes/no, see Appendix I, page 31-32), RMM tool mentioned (yes/no), type of RMM tool (SmPC, package leaflet, visual reminders on packaging, HCP guide/checklist, patient guide, patient card, annual risk acknowledgement form, DHCP, and suspension), recommendations in relation to RMM included (yes/no), clinical action related to RMM (yes/no, see list in Appendix I), explicit mention of reference for RMM information (yes/no), reference (in case explicit mention of reference is yes).

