## 9. Research methods

### 9.1. Study design

This qualitative study will employ a multiple-case study design using document analysis of clinical guidelines combined with qualitative interviews with key informants from the organizations/entities that produce guidelines in these specific countries as well as representatives from national competent authorities. Case study is a research design that has been widely used in social science research. In this study, we use a sub-type that is a multi-case design - in contrast to a single case design - which includes multiple cases selected according to a case selection strategy that aligns with the aims and objectives of the research. This study employs a diverse case selection strategy which is characterized by the selection of a set of cases intended to represent the full range of values along at least two dimensions (12). In this study the two dimensions are the five RMMs/TAs and the six countries outlined above. The purpose of selection strategy is to represent a maximum range of geographical diversity across EU members countries as well as maximum range of diversity of stakeholders across therapeutic areas that may be subject to RMMs. By contrasting and comparing the cases in the multi-case design, we learn about commonalities and variations. We also illuminate the potential reasons for these variations. The diverse-case selection strategy enables an in-depth of understanding of RMM implementation including its variation across the EU, which, in turn, allows for the identification of problems to deal with through research or regulatory intervention.

The combination of document analysis followed by semi-structured interviews utilizes the capacity of qualitative interviewing to explore subjective, non-observable dimensions of social relations or work processes to supplement and extend understanding of the results from preceding document analysis (13). The use of two sources of data also allows an ongoing validity assessment based on the convergence of information from the two sources.

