## **9.6. Data management**

A data management plan (DMP) will be created for the collection, extraction, transformation, loading and analysis of all data. Moreover, we will consider privacy related issues and facilitate a Data Protection Impact Assessment (DPIA). The DMP describes data that will be acquired or produced during research; how the data will be managed, described, and stored, what standards will be used, and how data will be handled and protected during and after the completion of the project. A DPIA is required under the EU General Data Protection Regulation 2016/679 (GDPR) any time a new project is started that is likely to involve “a high risk” to other people’s personal information. The DMP and DPIA will be conducted prior to the roll out of the project once the countries’ analysis plans are finalized.

Information materials will be obtained through the organizations’ website and a domain-specific query using a proprietary search engine (Google Inc.) in which active ingredients and class names are used as search strings. Previous experience showed that relevant documents may be available online but only through search mechanisms. Key informants will also be asked about additional information materials in interviews. All organisations are contacted to ask if they have produced any other relevant documents in addition to those retrieved. Finally, if the websites have a search bar it will be used to search for each medicinal product and medicinal product class as listed in the safety advisory.

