## **9.7. Data analysis**

A coding framework will be created by the coordinating team and national teams for the document analysis before reading the material to gather the information considered relevant based on the RMM for each of the five disease priority areas and active substances. The coding framework can be expanded and amended once a few documents have been reviewed and differences between them identified. Information products will be aggregated according to their source and similarity. The extent to which information products cover the RMM will be graded based on the results of the coding of information products.

Interview transcripts (text) from semi-structured interviews with stakeholders (representatives of key bodies and organisations) will be produced. The analysis of the semi-structured interviews involves an inductive content analysis based on a close line-by-line reading of the responses and developing a conceptual coding scheme based on the major themes in the interview guide. First five transcripts will be categorized individually by two coders in each country in native languages. The transcripts will be compared, discussed and if needed a third researcher will be consulted. Coders from all countries will meet prior to the analysis to predefine categories and codes to be used. They meet again to evaluate the categories identified and to write up the results using illustrative quotes.

The process for updating clinical guidelines, based on results from WP2 and WP3 will be presented in a visualized manner, e.g., using process maps

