	
each patient's potential for becoming pregnant, - pregnancy tests before starting and during treatment as needed, - counselling about the risks of valproate treatment and the need for effective contraception throughout treatment, - a review of ongoing treatment by a specialist at least annually, - introduction of a new risk acknowledgement form that patients and prescribers will go through at each such annual review to confirm that appropriate advice has been given and understood.
	
bacterial (chronic) prostatitis; - for preventing traveller's diarrhoea or recurring lower urinary tract infections (urine infections that do not extend beyond the bladder); - to treat mild or moderate bacterial infections unless other antibacterial medicines commonly recommended for these infections cannot be used. Importantly, fluoroquinolones should generally be avoided in patients who have previously had serious side effects with a fluoroquinolone or quinolone antibiotic. They should be used with special caution in the elderly, patients with kidney disease and those who have had an organ transplantation because these patients are at a higher risk of tendon injury. Since the use of a corticosteroid with a fluoroquinolone also increases this risk, combined use of these medicines should be avoided.
	
-To avoid confusion, recommendations to split the dose should be deleted from the product information for the tablet formulation. -Packaging for all methotrexate-containing medicines for once-weekly use to include a prominent reminder of how the medicine should be used. -Patient card emphasising the weekly dosing for inflammatory diseases to be provided with oral medicines. -Healthcare professionals to be provided with educational materials for oral medicines and to counsel patients accordingly. -Tablets to be available in blister packs instead of bottles (or tubes) in order to help patients follow the once-weekly dosing.
	
possible increased risk in these patients. The contraindication for patients with severely reduced kidney function will remain (GFR less than 30 ml/min). Reduced doses should be considered for patients with moderate reduction of kidney function according to dosage recommendations provided in the updated product information. The product information also details risk factors for lactic acidosis which should be reviewed prior to and during treatment.
	
related medicines, capecitabine and tegafur

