	Go through risk acknowledgement form at each annual review	Do not use in patients who have had a serious adverse reactions associated with quinolone or fluoroquinolone medicines		Fixed-dose combination canagliflozin/metformin (Vokanamet) are not recommended when GFR<45 ml/min	Treatment is contraindicated in patients with complete DPD deficiency (flucytosine)
	Do not start therapy unless alternative treatments are not suitable (including girls below age of puberty)			Fixed-dose combination empagliflozin/metformin (Synjardy) are not recommended when GFR<45 ml/min	Treatment should be stopped in case of drug toxicity (flucytosine)
	Women and girls who have been prescribed valproate should not stop taking their medicine without consultation			Fixed-dose combination canagliflozin/metformin (Vokanamet) should not be started when GFR<60 ml/min	
	If a woman using valproate becomes pregnant, she must be immediately referred to a specialist to re-evaluate treatment with valproate and consider alternative option			Fixed-dose combination empagliflozin/metformin (Synjardy) should not be started when GFR<60 ml/min	
	A patient guide and a patient card should be provided to all women of childbearing potential			In patients with GFR of 60-89 mL/min, maximum daily dose (MDD) of 3000 mg divided in 2-3 doses per day; dose reduction may be considered in relation to declining renal function	
				In patients with GFR of 45-59 mL/min, MDD	

				of 2000 mg divided in 2-3 doses per day	
				In patients with GFR of 30-44 mL/min, MDD of 1000 mg divided in 2-3 doses per day	
				Starting dose at most half of the maximum dose in patients with GFR of 30-59 mL/min”	

\*This table includes the tools for risk minimisation which EMA has considered most relevant to integration in clinical guidelines in their request for information to Member States but does not include a complete list of all RMM tools required by PRAC for the case examples.

\*\* For complete information on overview of the measures taken for each active substance see links below:  
<https://www.ema.europa.eu/en/news/new-measures-avoid-valproate-exposure-pregnancy-endorsed>  
<https://www.ema.europa.eu/en/medicines/human/referrals/quinolone-fluoroquinolone-containing-medicinal-products>  
<https://www.ema.europa.eu/en/news/prac-recommends-new-measures-avoid-dosing-errors-methotrexate>  
<https://www.ema.europa.eu/en/news/use-metformin-treat-diabetes-now-expanded-patients-moderately-reduced-kidney-function>  

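### WP2 codes RMM integration only from text that is present, so a guideline that silently dropped fluoroquinolones for a restricted indication looks the same as one that did nothing

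*Protocol*

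**What the plan says.** Section 9.3 (WP2) lists what is extracted from each guideline. The RMM items are yes/no: "RMM mentioned (yes/no, see Appendix I, page 31-32), RMM tool mentioned (yes/no"), then "recommendations in relation to RMM included (yes/no), clinical action related to RMM (yes/no, see list in Appendix I"). Safety information and a reference are recorded in the same way when present. A separate field records "treatment (active substance: valproate, fluoroquinolones), methotrexate, metformin, fluorouracil and related substances"; its listed values do not include none or withdrawn. No listed variable compares a current version with the version before the RMM.

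Section 9.7 states: "The extent to which information products cover the RMM will be graded based on the results of the coding" of the information products. Section 9.2.2 says current versions are assessed and that elapsed time is noted where possible. Section 9.9 says WP2 will give no qualitative account of how RMMs are represented.

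Appendix I (Measures) gives four indication-based restrictions for fluoroquinolones. The fourth is conditional: the class is not to be used "to treat mild or moderate bacterial infections unless other antibacterial medicines commonly recommended for these infections cannot be used".

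On retrieval, section 9.1 (WP2) searches on ingredients, class names and indications of use, and asks issuers for prior versions. Section 9.6 describes the search as one "in which active ingredients and class names are used as search strings", without indications.

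**The concern.** Objective 2 asks how RMMs have been integrated into guidelines. A presence code answers that well when adopting the RMM means adding something, such as a DPD test, a weekly-dosing instruction or a renal dosing step. It answers badly when adoption can mean that a recommendation disappears. A guideline that took fluoroquinolones out of its options for a restricted indication, and gave no reason, scores no on every RMM item.

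Three planned outputs are affected:

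- The comparison between therapeutic areas (section 8, objective 1d; section 9.3) would set a measure that can miss adoption for one RMM against measures that largely cannot for the others.
- The time from national implementation to uptake in guidelines (section 9.1, WP2) would have no coded event to count to.
- The interviews, which build on the document findings, could start from the premise that an issuer had not acted.

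**Working it through.** The protocol states no figure on this point. It describes itself in these terms: "This qualitative study will employ a multiple-case study design using document analysis of clinical guidelines combined with qualitative interviews". There is no sample size or power statement to reproduce, so the check is mainly one of logic.

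**Step 1. What the codes return.** Take one restricted fluoroquinolone indication and five possible guideline histories.

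| History | RMM items in section 9.3 |
|---|---|
| A. Recommended before; restriction now stated | yes |
| B. Recommended before; removed, reason given | yes |
| C. Recommended before; removed without comment | all no |
| D. Recommended before; unchanged, no safety text | all no |
| E. Never recommended | all no |

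C, D and E share one pattern. The active-substance field helps only partly. If the class is gone from the whole document, the field may separate C from D, but it cannot separate C from E. If the class is kept for some other use, the field is filled in for C as it is for D.

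**Step 2. Does the clinical-action list help?** Appendix I gives six fluoroquinolone clinical actions: older age, renal impairment, solid organ transplantation, corticosteroid use, stopping at first symptoms, and earlier serious reactions. None is one of the four indication restrictions. Adding them would not be enough, because a presence item still needs text about the medicine.

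**Step 3. Direction and possible size (assumed inputs).** Among guidelines that recommended the class for a restricted indication before the RMM, let *T* be the share that adopted the restriction and *d* the share of those adopters that did so by silent removal. If the items were tallied as a proportion:

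- coded share = *T*(1 − *d*)
- shortfall = *T* × *d*

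With *T* = 60%:

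- *d* = 10%: 0.60 × 0.90 = 54%
- *d* = 25%: 0.60 × 0.75 = 45%
- *d* = 50%: 0.60 × 0.50 = 30%

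Over *T* = 40–80% and *d* = 10–50%, the shortfall runs from 0.40 × 0.10 = 4 points to 0.80 × 0.50 = 40 points. It is never negative. The documents give neither *T* nor *d*.

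**Step 4. What a separate category buys.** At *T* = 60% and *d* = 25%, text-based integration is 45% and silent removal by adopters is 0.60 × 0.25 = 15%. Reporting both brackets the answer between 45% and 45 + 15 = 60%. If a further share *u* of guidelines dropped the class for unrelated reasons, counting every removal as integration would give *T* + *u*, which is too high. Silent removal should therefore stand alone and not be added to either side.

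**The case against.** The best reply is that WP2 asks which RMM information guidelines contain, and a silent guideline contains none, so no is a correct code. That is fair for the code itself. It does not cover reading the resulting grade as integration and comparing it across therapeutic areas.

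It can also be said that the coding framework was piloted, may be amended after the first documents (section 9.7), and is followed by interviews meant to clarify document findings. All of this stands as opportunity: a removal could come to light. But no listed variable or rule directs anyone to look for one.

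Some stronger readings are tempting, and the documents do not support them:

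- *Such guidelines will not be retrieved.* A reader of section 9.6 alone might infer this. Section 9.1 already searches by indication, uses issuers' websites and contacts every issuer. What remains is a mismatch between two descriptions of the search.
- *Valproate has the same problem.* The entry "Do not start therapy unless alternative treatments are not suitable (including girls below age of puberty") might suggest so. But the valproate RMM is a conditional programme with counselling, testing, annual review and a risk form. Deleting the medicine conveys none of these, so a no is largely right.
- *All six fluoroquinolone country cases are fully affected.* Each case covers guidelines from several specialties. Only those on a restricted indication that dropped the class silently are touched, and nothing shows how many there are.
- *Every removal is adoption.* Silence gives no reason, and some removals may have nothing to do with the RMM.

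**Conclusion.** The point holds for the fluoroquinolone restrictions by indication. As listed, the WP2 RMM items cannot separate silent removal after the RMM from inaction or from never having recommended the class. Any resulting error in measured integration is downward, and it falls on this RMM more than on those that add text. The percentages above illustrate direction and rest wholly on assumed values; the actual size cannot be determined from the documents and may be small. The protocol also sets no adoption proportion and no explicit grading rule, so it would go too far to say that the plan will report a particular wrong figure. This is an inexpensive improvement that changes what WP2 can conclude, not a flaw in the study design.

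**What to change.** For each restricted fluoroquinolone indication in Appendix I, add two codes to the WP2 framework:

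1. Class recommended in the last pre-RMM version: yes / no / unknown.
2. Class recommended in the current version: yes / only when alternatives are unsuitable / not listed.

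Report two categories separately: removed after the RMM without a stated reason, and not listed with earlier status unknown. Count neither as non-integration, and neither automatically as integration. For the first, add a WP3 question on whether the RMM prompted the removal.

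Bring the search description in section 9.6 into line with section 9.1, which already includes indications of use.

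The cost is a little extra coding for one of the five RMMs, using prior versions that WP2 already requests. The drawback is an unknown category wherever no prior version is obtained. The change concerns classification only and takes no position on how the medicine should be used.
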